General Background: Binge drinking is a major public health problem in the United States. The Center for Disease Control (CDC) places alcohol as the number three cause of preventable deaths following nicotine use and overweight (Mokdad et al, 2004). Binge drinking, generally defined as the consumption of five or more standard drinks for a man or four or more drinks for a woman in about a two hour period (see Courtney and Polich 2009), is a major component of excessive alcohol use and a serious problem for the United States. The CDC (2012) report indicated that 17.1% of the adult U.S. population reported one binge drinking episode in the past 30 days in 2010--men (23.2%) vs. women (11.4%) with peak ages 18-24 years (28.2%), 25-34 years (27.9%), and 35-44 years (19.2%). Men reported an average of 5 binge drinking episodes/month with a mean of 9.0 drinks/episode and women 3.2 binge drinking episodes/month at 5.9 drinks/episode. Binge drinking leads to multiple problems, e.g. accidental injury (Gmel et al, 2006), aggressive and violent behavior (Shepard et al, 2006), and high blood pressure (Fan et al, 2008). Additionally, there is increased risk for developing alcohol dependence in individuals that binge drink frequently (Hingson et al, 2006). Overall, binge drinking contributes to more than half of all deaths attributed to alcohol and to three quarters of the economic cost of excessive alcohol use—*binge drinking is a serious public health problem and one that may exceed traditionally defined alcohol dependence in its overall cost to society.*

Binge drinking is a complex construct as it is both a stand-alone phenomenon and also a component of alcohol use disorders. We are focusing on the behavior to allow greater fidelity to the preclinical data where the key behavior was consumption of an intoxicating amount of alcohol in a two hour period, a non-dependent

model (Navarro et al, 2015). The majority of binge drinkers do not have physical dependence (see Woerle et al, 2007), and we are particularly interested in this "developmental" phase towards overt physical dependence as the preclinical literature suggests this phase may be a key time for clinical intervention (Thiele 2012).

Treatment of Binge Drinking with or without Co-Occurring Alcohol Use Disorders

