Participants: 50 men and women between the ages of 18 and 44 years of age will be recruited from social media, e-mail list serve to UNC students and staff, and local newspaper/radio advertisements. Key Inclusion criteria: 1) A minimum of 5/3 (men/women) or more binge drinking episodes per month over the past three months (mean population values, CDC (2012)). A binge drinking episode is defined as the consumption of 5/4 (men/women) standard drinks (~12 gms ethanol) in about a two-hour period. Requiring multiple episodes of binge drinking over several months is important to identifying subjects with a consistent pattern of bingedrinking as shorter time frames may give misleading information (see Courtney and Polich, 2009). Subjects may meet DSM-V criteria for mild or moderate alcohol use disorder; 2) BMI ≥18.5 (normal weight or above); 3) express a desire to achieve abstinence or to reduce alcohol consumption. Exclusion criteria: 1) Presence of physical dependence on alcohol as assessed by clear tolerance to alcohol or alcohol withdrawal symptoms based on SCID interview or a Severe Alcohol Use Disorder (>5 SCID DSM-V symptoms); 2) a history of bulimia or a seizure disorder; 3) clinically significant medical disease that might interfere with the evaluation of the study medication or present a safety concern (e.g., renal insufficiency, cirrhosis, unstable hypertension, diabetes mellitus); 4) clinically significant psychiatric illness including any psychotic disorder, bipolar disorder, anorexia/bulimia, severe depression, or suicidal ideation; 5) other substance abuse or dependence disorder other than nicotine or occasional cannabis use; 6) Concurrent use of anticonvulsants, varenicline, MAOIs, any anti-alcohol medication or any psychotropic medication with the exception of stable doses of antidepressants for one month; prior history of adverse reaction to bupropion or naltrexone; 7) AST or ALT > 3.5 times ULN or bilirubin > 1.5 X ULN; 8) positive urine toxicology screen with the exception of cannabis. Individuals with positive cannabis screens will be excluded only if they have a history of a cannabis use disorder; 9) pregnancy or breastfeeding.

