Recruitment, Telephone Screen, and Full Eligibility Screening: Subjects will initially be prescreened by phone and then at full screening read and sign the informed consent. A breathalyzer test will be administered (must be 0.00 gms/dl to give informed consent), height, weight and BMI recorded and a medical history and examination completed. Over-the-counter and prescription medication use will be recorded and nicotine use documented (Heatherton et al, 1991). CBC with differential; serum bilirubin, AST, ALT, GGT, sodium, potassium, chloride, blood urea nitrogen, creatinine, glucose; and urinalysis and urine toxicology completed. Women will be given a urine pregnancy test (U β -HCG) at screening and at weeks 4, 8, and 12 and at the initial treatment visit if it is more than 10 days from the screening visit. Trained interviewers will conduct the psychiatric screening interview using the M.I.N.I. (Sheehan et al., 1998). The SCID Substance Use Disorders Module to establish DSM-V criteria for alcohol use disorders (First et al, 2016) will be administered by either [name] o another doctor listed on the IRB protocol. The study coordinator will conduct the pretreatment 90day Timeline Followback (TLFB) interview to identify amount of alcohol consumed and timeframe of consumption (Sobell et al, 1988 and personal communication). A binge drinking episode requires a minimum of 5/4 (men/women) standard drinks consumed over about a two hour period, i.e. consuming a bottle of wine over five hours would not be coded as a binge drinking day. The Penn Alcohol Craving Scale (PACS) (Flannery et al, 1999) and the University of Rhode Island Change Assessment (URICA) (Diclimente and Hughes, 1990) will be completed and treatment goal—abstinence vs. reduction— recorded.

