Medical Management Intervention: The psychosocial support for the study will be Medical Management (MM) (Pettinati et al, 2005). Drs. [name], [name], [name] and [name] will conduct MM. Drs. [name] and [name] have been trained in MM by [name] and again by [name] of the University of Pennsylvania where [name] was trained as well. [name] has been trained in MM by [name]. MM sessions average 10-15 minutes and focus on three main areas: (1) feedback on consequences of drinking; (2) encouraging compliance with medication/addressing compliance problems and (3) encouraging progress towards drinking goal— reduction or abstinence are acceptable. 10% of sessions will be audiotaped and reviewed to enhance fidelity.

Medication Compliance Monitoring: Participants will record their pill taking in calendar-style diaries that will be provided and collected at each visit. Pills will be distributed in blister packs that will be returned to the study coordinator to reconcile any unused medication from the returned blister packs with participants' diary records.

Statistical Plan and Data Analysis

Outcome Variables: Key outcome variables include frequency of binge drinking, intensity of binge drinking, treatment response, and GGT levels. Frequency is assessed as number of binge episodes/time in trial controlling for missing data (see Statistical Analysis). Intensity of binge drinking is the number of drinks/binge drinking day. Response is defined as no binge drinking in final 6 weeks. Consequences of binge drinking and craving for alcohol will be examined.

Sample Size per Group: In the assessment of feasibility, we need sufficient size to fit our respective models and ensure adequate coverage of our confidence intervals. VanVoorhis and Morgan (2007) provide guidance with respect to minimal sample size needed for differences between groups. They recommend that the groups be no lower than 7 per cell. Our aim is on the effectiveness of bupropion versus placebo in addition to the examination of a potential moderation effect attributable to nicotine use. Assuming a 2:1 ratio between nicotine usage, a sample size of 30 per arm should ensure at least 7-10 per treatment arm as a function of nicotine use. Additionally, our proposed sample size of 30 per treatment arm is in agreement with Sugden et al. (2002) minimum sample size to ensure adequate coverage of nominal 95% confidence intervals, which require n> 28 under minimal skew.

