Statistical Analysis: Study participants will first be characterized on baseline measures with appropriate methods. We will derive weekly summary scores from the TLFB quantifying the %Binge Drinking Days and the average drinks per binge drinking day per week. Descriptives and exploratory graphing will be used to assess the presence of skew and/or outliers with appropriate transformation implemented as needed. As stated above, our sample sizes are set to assess feasibility and implementation; therefore, the respective analyses, are exploratory, and therefore, not powered, but analyzed in accordance with the methods and recommendations per Kianifard & Islam (2011) for this proof-of-concept study. Per recommendation 4 of Kianfiard & Islam (2011) who describe caution when interpreting analyses from small trials, we will implement

IRB #16-1064 Master Protocol v.3

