an analytical procedure which maximizes the statistical power. The Institute of Medicine recommends several approaches, including clustered models, to maximize information from small trials and increase statistical power (Institute of Medicine, 2001). Using the full sample (N=50), we will fit a Mixed Effects Model (MEM) (Schwarz, 1993)) on: %Binge Drinking Days, drinks/binge drinking day, GGT outcomes with the focus on the linear contrasts within the MEM framework examining the superiority of bupropion to placebo. Our modeling will not focus on statistical significance but rather derive confidence intervals for the respective contrasts within the MEM framework examining the superiority of bupropion to placebo MEM accommodates the within-subject correlation of the repeated assessments (weekly for TLFB measures). MEM allows for the inclusion of potential predictors and covariates such as cotinine levels, medication compliance, demographics, and baseline clinical measures such as motivation. Pattern-mixture models (Hedeker & Gibbons, 1997 & 2006) will be used within the MEM structure to assess whether linear contrasts are dependent on attrition/missing data patterns. The pattern-mixture model is dependent on the number of distinct missing data patterns. With this limited sizes study, we will define the patterns as completers vs non-completers as was done by Hedeker & Gibbons (1997,2006). An assessment of significance will not be made but rather we will derive effect sizes of the respective bupropion and placebo contrast for both completers and dropout. With the limited sample and therefore, limited sample per pattern, we realize the respective confidence intervals will be wide. An additional benefit of the MEM is, it will allow us to assess for possible moderators. A moderator is a baseline measure or prerandomization characteristic that has a differential effect on outcome across intervention condition (Kraemer et al., 2002). Moderators are typically defined as variables that significantly interact with condition (Baron & Kenny, 1986; Holmbeck, 1997). The particular moderator of interest is use of nicotine. Assessment of moderation will be made by augmenting our MEM outcome analyses to include the interaction of the effect of assignment (bupropion vs placebo) intervention with the use of nicotine. In a sufficiently sized study, we will have a significant moderator of the assignment effect if the interaction term is significant (Kraemer et al., 2002), where statistically significant interactions would be interpreted by plotting simple regression lines for use versus non-use of nicotine (Holmbeck, 1997; Aiken & West, 1991). With the small sample, we will derive a confidence interval for the respective interaction effect, namely the difference of the differences (the difference between buproprion versus placebo for nicotine users versus the difference between buproprion versus placebo for the nicotine abstainers). Subsequently, we will perform a corroborative set of analyses, in accordance with Kianfiard & Islam (2011), where summary measures over the entire TLFB period are derived. Simple ANOVA/ANCOVA models will be used to perform the above analyses with the model structure producing confidence intervals for both the buproprion versus placebo contrast, as well as the moderation assessment.

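### Weekly drinks per binge drinking day has no value in binge-free weeks and a floor at 5/4 drinks, so its bupropion-placebo interval is conditional on bingeing and does not estimate the effect of assignment

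*Combined protocol and SAP*

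**What the plan says.** Outcome Variables lists four key outcomes: binge frequency, binge intensity, response and GGT. It defines the second thus: "Intensity of binge drinking is the number of drinks/binge drinking day". Response means having no binge in the last 6 weeks.

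Statistical Analysis turns the TLFB into weekly scores, "quantifying the %Binge Drinking Days and the average drinks per binge drinking day per week", and the mixed effects model is fitted to "Binge Drinking Days, drinks/binge drinking day, GGT outcomes with the focus on the linear contrasts within the MEM framework". The product is a confidence interval for bupropion against placebo. The moderation text describes this contrast as the effect of assignment.

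The eligibility screening section sets the floor: "A binge drinking episode requires a minimum of 5/4 (men/women) standard drinks consumed over about a two hour period".

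Two further provisions bear on the point. For the pattern-mixture model, "we will define the patterns as completers vs non-completers". In the corroborative ANOVA/ANCOVA, "summary measures over the entire TLFB period are derived".

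Neither Outcome Variables nor Statistical Analysis says what value a week without a binge takes. No planned outcome measures the amount drunk in every observed week.

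**The concern.** Three features of the intensity outcome combine.

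- **Undefined weeks.** With no binge day in the week, the average is 0/0. A responder supplies no intensity data for the final 6 weeks.
- **Selection after randomisation.** Whether a week has a value depends on the frequency outcome, which the drug is meant to change. The arms then contribute different kinds of people and weeks, and randomisation no longer protects the comparison. Splitting completers from non-completers deals with dropout, not with a completer's binge-free weeks.
- **Truncation.** The measure cannot fall below 5 drinks for men or 4 for women. A drinking day reduced to below the threshold leaves the average and is not counted as an improvement.

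The plan sets significance aside in favour of intervals and effect sizes, so the estimates are its main product. What is at stake is a misread effect size for one of four key outcomes. No significance decision is at stake.

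**Working it through.** The plan gives no figure for this outcome (no SD, effect size or expected share of empty weeks), so there is none to reproduce.

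**1. Binge-free weeks**

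Input, from Key Inclusion criteria: "A minimum of 5/3 (men/women) or more binge drinking episodes per month over the past three months". With m binges per 30 days occurring independently, the chance of an empty week is exp(-7m/30) (Poisson) or (1 - m/30)^7 (binomial, at most one binge a day). For m = 5 these are exp(-1.167) = 0.311 and (0.8333)^7 = 0.279.

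| Rate | Men: m | Empty weeks (Poisson / binomial) | Women: m | Empty weeks (Poisson / binomial) |
|---|---|---|---|---|
| Entry minimum | 5 | 0.311 / 0.279 | 3 | 0.497 / 0.478 |
| Minimum, halved | 2.5 | 0.558 / 0.544 | 1.5 | 0.705 / 0.698 |
| Twice the minimum | 10 | 0.097 / 0.059 | 6 | 0.247 / 0.210 |

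Halving twice the minimum returns to the first row. In each case the share without a value moves with the treatment effect.

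Over all 84 days at half the minimum rate, the chance of no binge at all is exp(-7) = 0.0009 for men and exp(-4.2) = 0.0150 for women (binomial 0.0007 and 0.0135). The whole-period summary is therefore defined for nearly everyone if rates are homogeneous.

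**2. Truncation**

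Assumed, because the documents give no distribution: drinks per drinking day follow a gamma distribution with mean 6, 7, 8 or 9 and SD 3 or 4, rounded to whole drinks. A binge day is any day at or above the threshold. Every day is lowered by 1 or 2 drinks, or cut by 30%. The visible share is the fall in the conditional mean divided by the shift, or the relative fall divided by 0.30.

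| Case | 1-2 drink fall | 30% cut |
|---|---|---|
| Threshold 5 | 14-69% | 53-81% |
| Threshold 4 | 19-84% | 63-92% |
| Men, conditional mean 9.0, SD 3-4 | 30-65% | 65-78% |
| Women, conditional mean 5.9, SD 1.5-2 | 32-62% | 60-72% |

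The last two rows are calibrated to the drinks per episode in General Background, "with a mean of 9.0 drinks/episode and women 3.2 binge drinking episodes/month at 5.9 drinks/episode"; their SDs are assumed. As an example, with mean 7, SD 3 and threshold 5, the measure goes from 7.95 to 7.58 after a 1-drink fall and to 7.30 after a 2-drink fall. On the threshold-5 grid, binge days fall by 7-43% under the same effects, which %Binge Drinking Days would record.

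**3. Which binges are removed**

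Removing binges at random leaves the measure unchanged. Removing 50% or 80% of the 5-7-drink binges (mean 7, SD 3) raises it from 7.95 to 8.64 or 9.36. In those cases binge alcohol falls 19.6% or 31.3%, and binge days fall 26.0% or 41.6%.

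**4. A second model**

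This is a 12-week simulation with a random-intercept mixed model on the weekly measure. Assumed: threshold 5, about 2.5 sessions a week, log-normal drinks with median 5, and log SDs of 0.30 between and 0.45 within persons.

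| Scenario | Drinks per session | Contrast, empty weeks missing | Contrast, empty weeks set to 0 |
|---|---|---|---|
| No effect | 5.76 vs 5.80 | +0.07 (SE 0.06) | +0.14 (SE 0.10) |
| Every session cut 25% | 5.79 to 4.35 (-1.44) | -0.81 | -1.77 |
| Every session cut 40% | 5.83 to 3.46 (-2.37) | -1.27 | -3.10 |
| Half of sessions under 8 drinks prevented | 5.80 to 6.75 | +0.74 | -0.53 |

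In the second row, 0.81/1.44 = 56% of the fall is visible. In the last row, total drinks per week fall from 14.79 to 10.27, yet the measure favours placebo. The unstated coding rule alone doubles one estimate and reverses another. The whole-period summary keeps the distortion: 7.35 vs 6.51 for the 25% cut, and 7.34 vs 8.02 in the last scenario.

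**The case against.** The strongest reply is that the plan never claims this contrast measures total amount drunk. Intensity is meant to be the size of a binge, and frequency and response are separate outcomes. An intensity measure ought to stay still when binges are removed at random. This has force, and it is why the measure should stay. It does not rescue the interval as an effect of assignment, because binge size is compared only in weeks selected by a post-randomisation event.

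Other points that stand:

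- The analyses are declared exploratory and unpowered.
- The whole-period ANOVA/ANCOVA largely removes the empty weeks. It does not remove the truncation or cover people who stop bingeing altogether.
- Entry rates are minima, and independent timing is assumed. Regular weekly bingeing would give fewer empty weeks, clustered bingeing more.
- The attenuation figures depend on assumed distributions. They use a daily-total cutoff that ignores the two-hour window, and the calibration applies general-population episode sizes to trial participants.
- The no-effect simulation showed no material bias, and reversal needs a drug that mainly removes the lightest binges. The documents give no reason to expect that.
- Total drinks may be noisier. An illustrative simulation (gamma mean 7, SD 3, 2 sessions a week, 30% cut, no baseline adjustment) gave standardised effects of 0.94-1.37 for drinks per binge drinking day and 0.46-0.79 for total drinks.

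These points limit the size of the harm and argue against replacing the measure. They do not change what the interval estimates.

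**Conclusion.** The concern holds. The undefined weeks, the floor at 5/4 drinks and the conditioning on a post-randomisation event follow from the plan's own definitions, with no distributional assumption. The share of empty weeks rests on the entry-minimum rates and independent timing: about 28-31% for men and 48-50% for women, falling to 6-10% and 21-25% at twice the minimum.

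The attenuation is illustrative. In every reduction case examined where all days are lowered, part of the fall is hidden, but the visible share ranges from 14% to 92%. Reversal is possible only under selective removal of light binges.

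The loss is partial, since %Binge Drinking Days would still show the fall in binge days. This is a change that should be made. It does not undermine the trial.

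**What to change.** Amend the Statistical Analysis section as follows.

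1. Add total drinks per week (or mean drinks per day) from the TLFB as a modelled outcome in both the mixed effects model and the ANCOVA. Enter zero for observed weeks without drinking, and leave unobserved weeks missing.
2. Base any effect-of-assignment conclusion about the amount drunk on that outcome.
3. Keep drinks per binge drinking day in the models, but label it as conditional on bingeing. State that binge-free weeks have no value, report contributing participants and weeks by arm, and interpret it only together with %Binge Drinking Days.

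The cost is SAP wording and one more outcome; no new data are needed. Total drinks mixes frequency with intensity, includes non-binge drinking, does not isolate binge size, and may be less precise under a proportional reduction. The conditional measure is kept for those reasons.

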**Trial Design**: The design is a 1:1 random assignment to placebo or bupropion XL (300mg/d). [name], the study biostatistician, will prepare the randomization schedule and include blocking by gender. Randomization will be based on a stratified block design, with gender and nicotine dependence as the IRB #16-1064 Master Protocol v.3

stratification variable given some evidence of a moderating effect of nicotine dependence on response to alcohol pharmacotherapy (Fucito et al, 2012).

Bupropion XL will be initiated at 150 mg/d on Days 1-4 and increased to 300 mg/d for Days 5-84. Medication is reduced to 150mg/day for 3 days before being stopped at Week 12 UNC Hospital's Investigational Drug Services (IDS) will prepare opaque capsules containing bupropion XL 150/300 mg and matching placebo. Capsules will be inserted into blister packs with each pack containing 1 week of medication. The IDS will receive the randomization schedule from our statistician [name] and prepare the blister packs according to the blocked schedule with blocking for gender

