
Response, i.e. no binge drinking days in final 6 weeks of medication, tolerability measured via retention time, and number of adverse events reported will be examined with Logistic regression, Cox-Regression, and Ordinal-regression models, respectively with the same contrast comparisons as above focused on the derivation of confidence intervals for the respective contrasts. Moderation of nicotine use will follow the procedure as discussed earlier, where the respective models will be augmented to include the interaction of nicotine use with assignment, with the derivation of the confidence interval for the differences as described above.

DATA MANGEMENT PLAN

The Database will be configured in Microsoft Access or Excel. Discrepancies will be examined and additional data checks completed as indicated. A closed and password-protected data entry system will be used and only

certified study personnel will be able to enter or edit data. Data and user stamping are used to create an audit trail. Range checks, review screens, and error trapping routines are built into the system as quality control procedures. Hardcopy data summaries will be available to the investigators for data analyses. As a final check on data integrity, the investigators and study coordinator will check these outputs against the raw data and resolve any discrepancies. We will be asking subjects to fill out self-ratings on a tablet mobile device. The ratings will be in the form of Qualtrics surveys. No identifying data will be entered into the tablet, just a subject ID number.

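### The pattern-mixture analysis states effect sizes within completers and within dropouts but no pattern-averaged contrast, so it gives no overall estimate that allows for informative dropout.

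*Combined protocol and SAP*

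**What the plan says.** All of this is in the Statistical Analysis part of the combined protocol and SAP, under Statistical Plan and Data Analysis.

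- **Main analysis.** "Using the full sample (N=50), we will fit a Mixed Effects Model (MEM"), with confidence intervals for the bupropion-placebo contrasts. It is not split by dropout pattern.
- **Check on missing data.** Pattern-mixture models are fitted within the mixed model "to assess whether linear contrasts are dependent on attrition/missing data patterns". Because the study is small, "we will define the patterns as completers vs non-completers".
- **Output of that check.** No significance test is planned; the team will "derive effect sizes of the respective bupropion and placebo contrast for both completers and dropout". On precision: "we realize the respective confidence intervals will be wide". No weights and no averaged estimate are named.
- **Corroboration.** ANOVA/ANCOVA models are fitted after "summary measures over the entire TLFB period are derived". These are not split by pattern either.
- **Retention.** The last paragraph of the section says that response, "tolerability measured via retention time, and number of adverse events reported will be examined with Logistic regression, Cox-Regression, and Ordinal-regression models, respectively", with the same treatment contrasts and confidence intervals.

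**The concern.** Whether a participant completes is known only after randomisation and may depend on treatment. The plan accepts this in two places: it analyses retention time by arm as a tolerability outcome, and it defines a moderator as something measured before randomisation, which completion is not. Bupropion completers against placebo completers is therefore not a randomised comparison, and the same holds for dropouts.

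Under a pattern-mixture model, the effect of assignment is the difference between two arm means, each averaged over that arm's own mix of completers and dropouts. The two stated effect sizes are ingredients of that figure and omit the mix. Two contrasts near zero could be read as showing that dropout does not matter when the arms differ because one loses more people.

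The Outcome Variables paragraph says that binge frequency will be assessed with control for missing data and points to this section. The pattern-mixture model is the only method there aimed at outcome-related dropout. As stated, it leaves the reader without an overall figure to set beside the main contrast.

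**Working it through.** **Inputs.** The plan gives no dropout rate, mean or standard deviation, so there is no figure of its own to reproduce on this point, and every outcome value below is assumed. From the documents: 1:1 allocation (Trial Design) and N=50 (Participants; Statistical Analysis), hence 50/2 = 25 per arm. The Sample Size per Group paragraph uses 30 per arm; that discrepancy is a separate matter and does not alter the argument.

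**Formula.** Let pB and pP be the dropout proportions on bupropion and placebo, with pattern means for completers (C) and dropouts (D):

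overall contrast = [(1 − pB)·mean(B,C) + pB·mean(B,D)] − [(1 − pP)·mean(P,C) + pP·mean(P,D)]

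**Main example (assumed).** Completers binge on 20% of days and dropouts on 50% in both arms; pB = 30%, pP = 10%.

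- Within completers: 20 − 20 = 0. Within dropouts: 50 − 50 = 0.
- Bupropion mean: 0.7×20 + 0.3×50 = 29. Placebo mean: 0.9×20 + 0.1×50 = 23.
- Overall contrast: 29 − 23 = 6 points against bupropion.
- With one common set of weights (average dropout 20%): 0.8×0 + 0.2×0 = 0. The weights must be arm-specific.

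**Range.** When both within-pattern contrasts are 0, the formula reduces to (pB − pP) × gap, where gap is the dropout mean minus the completer mean. For an assumed gap of 20 points:

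| Dropout, bupropion v placebo | Within-pattern contrasts | Overall contrast (points) |
|---|---|---|
| 20% v 20% | 0 and 0 | 0 |
| 20% v 30% | 0 and 0 | −2 |
| 20% v 40% | 0 and 0 | −4 |
| 10% v 40% | 0 and 0 | −6 |
| 40% v 20% | 0 and 0 | +4 |

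For 20% v 40%, gaps of 10 to 30 points give −2 to −6.

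**What the other planned analyses would show.** A random-intercept mixed model was simulated on 12 weekly values. Assumptions: between-subject SD 10, within-subject SD 15, dropouts last seen between weeks 2 and 8, variance components supplied.

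- Main example: the full-sample contrast averaged 5.4 to 5.6 of the true 6 points, with a standard error of about 4.4 at 25 per arm. An unweighted comparison of per-person summary means gave about 6.
- Gap 20, dropout 20% v 40%: about −3.4 of −4.0. Dropout 10% v 40%: about −5.4 of −6.0. Standard error about 4.1 in each.
- Retention by Cox regression, main example: hazard ratio ≈ ln(0.7)/ln(0.9) = 3.39; events 25×0.3 + 25×0.1 = 10; SE of log HR ≈ 2/√10 = 0.63; 95% CI about 0.98 to 11.7.

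**Precision of the averaged contrast, main example.** The uncertainty in the two proportions alone contributes a standard error of 30 × √(0.3×0.7/25 + 0.1×0.9/25) = 30 × √0.012 = 3.3 points, before any uncertainty in the pattern means. The expected dropout cells are 25×0.3 = 7.5 and 25×0.1 = 2.5 people. If 2 of 25 in an arm drop out, a bootstrap resample of that arm contains no dropout with probability (23/25)^25 = 0.12.

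**The case against.** The strongest reply has four parts.

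1. **Other analyses see unequal dropout.** A reader might infer from the example that an effect acting through dropout is invisible to the plan. The documents do not support that. Retention is compared between arms directly, and the full-sample mixed model and the ANOVA/ANCOVA are not split by pattern. In the simulations the mixed model recovered most of the difference. This part stands, and it confines the point to the pattern-mixture output. It does not close the gap. The Cox model shows whether retention differs, not what that does to the drinking contrast, and the mixed model relies on missing at random.
2. **The model is offered as a diagnostic.** The stated aim is to see whether contrasts vary by pattern, and pattern-specific contrasts answer that. The plan does not present them as the effect of assignment. This is fair. But contrasts that agree across patterns do not show that the overall contrast is unaffected by dropout, as the example demonstrates.
3. **The cited method may include averaging.** A reader might infer that the plan rules out recombining the patterns. It does not: it cites a published pattern-mixture approach, and the documents cannot settle whether averaging is part of it. What can be said is that no averaging step is stated.
4. **Low yield.** The analyses are declared exploratory and unpowered, and dropout cells will be small. That stands as a limit on precision. In the constant-mean example the averaged contrast would also largely repeat the mixed model and the summary-measure comparison. It adds more where the outcome course of dropouts diverges from that of completers.

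**Conclusion.** The point holds in a limited form. As stated, the pattern-mixture analysis yields two non-randomised contrasts, omits the arm-specific dropout proportions, and gives no overall treatment estimate allowing for informative dropout. Under the assumed values it would report 0 and 0 where the arms differ by 6 points; over the other combinations tabulated the hidden difference runs from 0 with equal dropout to 6 points in either arm's favour, depending on the gap and on which arm loses more people. These sizes rest wholly on assumed means and dropout rates.

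The conclusion should not be stretched to say that the plan as a whole would miss such a difference. Its other analyses would show most of it, imprecisely, with the mixed model doing so under the assumption that this check is meant to probe. For an exploratory trial this is a worthwhile, inexpensive addition and not a flaw that undermines the main analysis.

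**What to change.** Keep the completer and dropout contrasts and label them descriptive. Then add to the Statistical Analysis section:

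- **Estimate.** For each arm, average its pattern-specific means using that arm's own observed completer and dropout proportions, and take the bupropion-placebo difference. Do not use weights common to both arms.
- **Interval.** Give a 95% confidence interval that includes the uncertainty in those proportions, by the delta method or by a bootstrap stratified by arm. Fix in advance what is done when a dropout cell is empty.
- **Reporting.** Present it as a sensitivity estimate beside the main mixed-model contrast, together with dropout numbers by arm. State that the dropouts' later weeks are extrapolated by the model.

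**Cost.** A few sentences of text and a modest amount of programming, including the empty-cell rule; no new data. The estimate will be imprecise: at 25 per arm, assumed dropout of 10% to 40% leaves only 2.5 to 10 people per dropout cell. The plan already accepts wide intervals for this analysis, so the addition fits its approach of reporting estimates without significance tests.
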